9.6.1 Obtaining Data Files

Not applicable

9.6.2 Linking Data Files

Not applicable

9.6.3 Review and Verification of Data Quality

Automatic edit checks within the database and further manual review by the sponsor help to ensure quality and completeness of the data. Data queries are sent to site for clarification and resolution of discrepancies.

Date: 29 April 2019 Page 35 of 64

9.7 Data Analysis

The analysis of this study will be descriptive in nature. Data will be summarised by appropriate descriptive statistics. Two-sided 95 confidence intervals will be presented where appropriate.

9.7.1 Planned Analyses

The baseline data will be summarized using descriptive statistics for subjects with mCRC who received panitumumab in combination with chemotherapy as 1st line treatment according to the type of chemotherapy received.

The data will be summarized for the total study population (all subjects with mCRC who received panitumumab in combination with chemotherapy as 1st line treatment) divided by the type of chemotherapy received: FOLFOX, FOLFIRI and others.

The data will be summarized for the total study population and per country. Further details will be provided in Statistical Analysis Plan (SAP).

9.7.1.1 Interim Analysis/Analyses

Not Applicable

9.7.1.2 Primary Analysis

Not Applicable

9.7.1.3 Final Analysis

The final analysis will occur when all enrolled subjects have completed the study.

9.7.2 Planned Method of Analysis

9.7.2.1 General Considerations

The analysis of this study will be descriptive in nature. Counts and percentages will be provided for categorical outcomes. Continuous outcomes will be summarized by the number of non-missing values, mean, standard deviation, median, lower and upper quartiles and minimum and maximum values. Time to event data will be analysed using Kaplan Meier estimator.

For each outcome parameter, the covariates listed in Section 9.3.3 may be assessed in a logistic or general linear model overall for the selected European countries where data is appropriate. If available, non-significant factors will be eliminated stepwise until only covariates significant at the 5% level remain, thereby indicating which covariates have an important influence on treatment pattern. Summary statistics will then be reported for each level of the significant covariates and will be subject to local data availability.

Date: 29 April 2019 Page 36 of 64

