9.3.2 Outcome Assessment

Primary outcomes

As primary outcomes the following data will be collected:

- characteristics of subjects with WT RAS non resectable mCRC receiving panitumumab in combination with chemotherapy as a 1st line treatment, including:
 - demographics: age, sex
 - targeted medical history: type of primary tumour and the date of diagnosis; site of primary tumour: rectum vs colon, right vs left colon; surgical procedures; lymph nodes: number and involvement; TNM stage; adjuvant chemotherapy, including regimen if applicable; sites of metastatic disease: liver, lung, other;
 - current status of mCRC: ECOG performance status, RECIST criteria (if available), ETS at week 8 (if available)
- pattern of treatment composed of:
 - 1st line treatment: agents and doses at baseline, any changes during
 1st line treatment, including dose, infusion schedule, and reasons for changes
 - 2nd line treatment: type of progression leading to 2nd line choice, type of 2nd line anti-cancer therapy, dose, schedule and reason for treatment selection

Secondary outcomes

In the secondary outcomes the following data will be gathered:

- Response to 1st line treatment measured as:
 - Death
 - Disease Progression
 - response rate (RR)
 - rate of conversion to resectable mCRC
 - tumour markers: CEA and CA 19.9
 - ETS (if available as per clinical practice) at week 8 measured by all or any of the following methods: CT, MRI, PET in comparison to the baseline.
- Safety assessments:
 - ADR reports related to panitumumab treatment
 - type and duration of ADR incident

Exploratory outcome

CCI

Date: 29 April 2019 Page 32 of 64

In study sites routinely performing biomarkers assessment in liquid biopsies, disease biomarkers information will be collected as per local regulations.

Since this is an observational study, all tests will be performed in line with routine clinical practice and no additional procedures are posed by the protocol.

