9.3.3 Covariate Assessment

Certain pre-treatment factors (covariates) may be found to affect the pattern of treatment with panitumumab in combination with chemotherapy, therefore covariates will be investigated to evaluate their influence. However, subgroup analysis will be performed based on availability of data.

The following covariates may be analysed:

- Demographic: body weight, age, sex
- Location of primary tumour: colon (right or left) vs. rectum
- oxaliplatin-based chemotherapy for mCRC: yes vs. no
- irinotecan-based chemotherapy for mCRC: yes vs. no
- country
- total

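### If the optional covariate model is fitted to the 1st line regimen as Section 9.7.2.1 allows, it is circular: the oxaliplatin and irinotecan indicators are both covariate and outcome

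*Protocol*

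**What the plan says.** Four statements in the Protocol have to be read together.

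- Section 9.7.2.1 sets the scope of the modelling: "For each outcome parameter, the covariates listed in Section 9.3.3 may be assessed in a logistic or general linear model overall". It then gives the selection rule, "non-significant factors will be eliminated stepwise until only covariates significant at the 5% level remain", and the interpretation, "thereby indicating which covariates have an important influence on treatment pattern".
- Section 9.3.3 introduces the list with "Certain pre-treatment factors (covariates) may be found to affect the pattern of treatment with panitumumab in combination with chemotherapy". The list contains "oxaliplatin-based chemotherapy for mCRC: yes vs. no" and "irinotecan-based chemotherapy for mCRC: yes vs. no", next to body weight, age, sex, primary tumour location and country.
- Section 9.3.2 places among the primary treatment-pattern outcomes "1st line treatment: agents and doses at baseline, any changes during" that treatment. Section 9.7.2.4 adds the type of chemotherapy given with panitumumab, and Section 9.7.1 groups it as FOLFOX, FOLFIRI or other.
- Table 2 names both backbones as exposure variables in the treatment-pattern row, whose first outcome is the 1st line treatment. Section 9.7.2.3.2 treats the oxaliplatin/irinotecan split as the treatment itself.

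No text exempts the 1st line regimen from the rule or removes the backbone indicators when the regimen is the outcome. Section 9.9.1.2 names both backbones among the confounders to be controlled in the analysis.

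**The concern.** The modelling is meant to show which pre-treatment factors influence the pattern of treatment. The backbone is not such a factor for the 1st line regimen, because it is the regimen in coarser coding. FOLFOX implies oxaliplatin = yes, and FOLFIRI implies irinotecan = yes. With these indicators in the model, the question changes from what drives the choice of regimen to what drives it among subjects who already share a backbone. Little of the choice is left to explain. What is at stake is any statement in the report about which patient or country characteristics influence 1st line regimen choice. Treatment pattern is part of the primary objective (Section 8.1).

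**Working it through.** **The plan's own figure.** The protocol gives no figure for this model. Its only precision figure is a 95% half-width of at most 4 percentage points at N = 600 (Section 4). It reproduces: 1.96 × √(0.25/600) = 0.0400. Only N = 600 is used below.

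**Step 1: are the indicators the study regimen or earlier treatment?** The abstract mentions covariates related to prior therapies, so the second reading has to be considered. It fails. Every subject is on 1st line treatment (Section 9.2.3.1). The indicators refer to chemotherapy for metastatic disease, which does not describe adjuvant therapy. Section 9.7.2.3.2 and Table 2 use them for the current treatment.

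**Step 2: the separation, by arithmetic.** Assume 60% of 600 subjects receive oxaliplatin (360) and 5% of those receive a regimen other than FOLFOX. The outcome is FOLFOX, yes or no.

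| | FOLFOX | not FOLFOX |
|---|---|---|
| oxaliplatin yes (360) | 342 | 18 |
| oxaliplatin no (240) | 0 | 240 |

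- Deviance without the indicator, p = 342/600 = 0.57: −2[342 ln 0.57 + 258 ln 0.43] = 820.0.
- Deviance with it: −2[342 ln 0.95 + 18 ln 0.05] = 142.9. The 240 subjects without oxaliplatin contribute zero.
- Likelihood-ratio statistic: 820.0 − 142.9 = 677.0 (from unrounded values), against a 5% critical value of 3.84.
- Deviance left: 142.9/820.0 = 17%. With 20% other regimens (288 and 72 of 360), 360.3/830.8 = 43% is left.

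What is left concerns FOLFOX against other oxaliplatin regimens, not oxaliplatin against irinotecan. The empty cell sends the oxaliplatin coefficient to infinity, so its standard error and Wald test are meaningless. If the outcome is the backbone itself, separation is complete.

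**Step 3: simulation with several covariates.** All inputs except N = 600 and the 5% level are assumptions.

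*Simulation 1.* 200 studies per scenario; likelihood-ratio backward elimination; covariates age, weight, sex, location (22% right-sided) and nine equal countries; about 60% FOLFOX before other regimens. The true effect is on right-sided location.

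| Other regimens | OR 2.0: kept without / with backbone | OR 1.8: kept without / with backbone |
|---|---|---|
| 5% | 89% / 7% | 74.5% / 11% |
| 10% | 81% / 2.5% | 70.5% / 1% |
| 20% | 73.5% / 6% | 61% / 3.5% |

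With no covariate affecting the choice, the oxaliplatin term was kept in 97.5% to 100% of runs and the irinotecan term in 100%.

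*Simulation 2.* One binary driver (OR 2, 50% prevalence), age as a null covariate, both backbone indicators.

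- Full models, 300 studies: the driver was significant in 97% (outcome FOLFOX) and 98.7% (outcome oxaliplatin backbone) without the indicators. With them it was significant in 6.7% and 0% by likelihood-ratio test, and in 5.3% and 0% by Wald test.
- In those models the oxaliplatin term was significant in 100% of runs by likelihood-ratio test and in 0% by Wald test. The fit converged in no run.
- Backward elimination, outcome FOLFOX, 150 studies per scenario, other regimens 5% or 20% of oxaliplatin users, both or neither backbone in 2% or 10% of subjects:

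| Test | oxaliplatin kept | irinotecan kept | true driver kept |
|---|---|---|---|
| likelihood-ratio | 100% | 2% to 6% | 1% to 7% |
| Wald | 0% | 31% to 99% | 27% to 73% |

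Whether the irinotecan term survives depends on the assumed regimen mix and on the test.

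**Step 4: outcomes after the choice.** For a binary outcome unrelated to the backbone (30% frequency), the backbone was significant in 5.2% of 500 runs, the nominal rate. Keeping it for such outcomes does no harm.

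**The case against.** The strongest reply is that no such model is prescribed. Sections 9.3.3 and 9.7.2.1 are permissive, further detail is left to the SAP, and Section 9.7.2.4 commits only to descriptive statistics for 1st line treatment. This stands in part: the circular model is allowed, not required. It does not dispose of the point, because the protocol itself fixes the list, labels it pre-treatment and extends it to every outcome parameter. An SAP that follows the protocol inherits the fault.

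Four stronger readings are tempting, and the document does not support them.

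- *The backbone will always be significant.* Section 9.7.2.1 names no test. The claim fits likelihood-ratio tests. Under Wald tests the oxaliplatin term is never significant, and the true driver sometimes survives.
- *Tumour location and country would drop out of the report.* Section 9.7.2.1 adds summaries for significant covariates and does not confine reporting to them. Table 2 and Sections 9.7.1 and 9.7.2.4 plan summaries by country and tumour location regardless.
- *The model tests a different null from the stated one.* The protocol states no null. Section 7.3 says no hypothesis is involved.
- *The whole covariate analysis is affected.* Only models of the 1st line agents or regimen are. For "2nd line treatment: type of progression leading to 2nd line choice, type of 2nd line anti-cancer therapy, dose, schedule and reason for treatment selection", and for 1st line changes and response, the backbone is a legitimate covariate.

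It is also fair to say that FOLFOX against the rest is a chosen outcome, since Section 9.7.1 has three categories, and that Section 9.3.3 sets colon (right or left) against rectum rather than using a right-sided indicator. These choices affect the simulated percentages but not the circularity.

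**Conclusion.** The point holds in a limited form. Sections 9.3.2, 9.3.3 and 9.7.2.1 together permit a model in which the 1st line backbone explains the 1st line regimen, and call that backbone a pre-treatment factor. Such a model cannot reliably identify what drives regimen choice, whichever test is used. That conclusion follows from the definitions and needs no assumption.

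The size does need assumptions: regimen mix, prevalence and strength of the driver, and type of test. Under those tried with OR 2, detection falls from 73.5% to 98.7% without the backbone terms to 0% to 7% with them by likelihood-ratio test. Wald elimination keeps the driver in 27% to 73%. These ranges illustrate the loss and do not forecast it for this study. The planned descriptive account of treatment patterns is untouched.

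**What to change.** In Sections 9.3.3 and 9.7.2.1, state that the oxaliplatin-based and irinotecan-based indicators are not entered in any model whose outcome is the 1st line agents or regimen. Such models use only age, sex, body weight, primary tumour location and country. Stop describing the two indicators as pre-treatment factors. Keep them for outcomes that follow the choice of regimen: 1st line changes, discontinuation, 2nd line treatment, response, progression, death and ADRs. Carry the same exclusion into the SAP.

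The cost is about one sentence. It needs no new data or subjects, and no meaningful analysis is lost.

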9.7.2.2 Missing or Incomplete Data and Lost to Follow-up

All available data collected during the retrospective and prospective observation periods, the safety follow-up period, and the end of study visit will be used in the analysis. The eCRFs will be designed to minimise missing data and to optimise the integrity of collected data. Subjects' records will not be excluded because of missing data and missing data will not be inputted. For categorical variables, missing responses will be shown as a separate category in the analysis. For numeric variables, the number of non-missing observations will be presented.

9.7.2.3 Descriptive Analysis

9.7.2.3.1 Description of Study Enrolment

All eligible subjects' enrolled into the study will be included in the full analysis set and will be included in all summaries and analyses. To assess whether sites are representative cross country, summary statistics of site characteristics and the number of subjects enrolled in the study by site will be provided.

9.7.2.3.2 Description of Subject Demographics/Subject Characteristics

Baseline (retrospective) data will be summarized for subjects with mCRC who received panitumumab in combination with chemotherapy as 1st line treatment according to the type of chemotherapy received and overall. The baseline data will also be summarized overall for the selected countries and by treatment (Oxaliplatin/Irinotecan based).

Baseline demographics/characteristics will be summarized using descriptive statistics. Demographic and clinical characteristics of subjects in the study outlined in Section 9.3.3 will be summarized. Measurements such as age will be calculated based on the subject status at the start of the Observation Period (Baseline), and clinical characteristics as morphological tumour changes, surgeries, hospitalization, new metastatic sites, etc. will be captured throughout the Observation Period.

9.7.2.4 Analysis of the Primary, Secondary and Exploratory Outcomes Primary Outcomes

Characteristics of subjects:

Descriptive statistics will be used to summarize subject demographic and baseline characteristics including age, sex, height, body weight, reproductive status, disease history, and current status of disease. The duration of Safety Follow-up will also be summarized.

Date: 29 April 2019 Page 37 of 64

Patterns of treatment:

Description of 1st line treatment, including type of chemotherapy combined with panitumumab, start and stop dates, dose, unit, route, frequency and reason for cessation of chemotherapy and/or Panitumumab will be summarized across the entire observation period using descriptive statistics.

Type of progression leading to 2nd line choice, type of 2nd line anti-cancer therapy including infusion schedule will be summarized using descriptive statistics.

Treatment patterns in relation to tumour location (left vs. right): frequency and percentage of subjects with left or right location of tumour will be provided.

Secondary Outcomes

Response to 1st line treatment:

Death and Disease Progression per Investigator assessment will be analysed using Kaplan Meier estimator.

Response rate (RR) and conversion to resectability will be summarized using descriptive statistics.

Tumour markers (CEA and CA 19.9) will be summarized descriptively for total population.

ETS (if available, per clinical practice) at week 8 will be provided.

Response rate, tumour markers, type of progression leading to 2nd line choice, type of 2nd line anti-cancer therapy and subsequent treatment line will be summarized descriptively according to the location of the tumour and current disease status.

Exploratory Outcomes

CCI

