Immunoglobulin	
institutional review board	
IR (irinotecan) OX (oxaliplatin)	
interactive voice response system	
Kirsten rat sarkoma 2 viral oncogene homolog, gen of RAS family	

Product: Panitumumab (Vectibix®) Protocol Number: 20170734 POWER Date: 29 April 2019

Date: 29 April 2019 Page 9 of 64

Abbreviation or Term	Definition/Explanation	
LV	Leucovorin, folinic acid	
mCRC	metastatic colorectal cancer	
MedDRA	Medical dictionary for regulatory activities	
MRI	magnetic resonance imaging	
NRAS	neuroblastoma RAS viral oncogene homolog, gene of RAS family	
ORR	objective response rate	
OS	overall survival	
OTC	over the counter	
PET	positron emission tomography	
PFS	progression-free survival	
PP	percentage points	
QoL	quality of life	
RECIST	response evaluation criteria in solid tumours	
RR	response rate	
SAP	statistical analysis plan	
SmPC	summary of product characteristics	
TGFα	transforming growth factor-alpha	
TNM	tumour node metastasis	
WT	wild type	
VEGF	vascular endothelial growth factor	
VEGFR	vascular endothelial growth factor receptor	
5-FU	fluorouracil	
Baseline Visit	The date of start of 1st line chemotherapy and panitumumab	
Enrolment Visit	The date of informed consent signature	
End of Observation Visit	The visit at the end of Prospective Observation Period or the last visit before death or withdrawal of informed consent or lost to follow-up	
End of Study Visit	The visit at the end of Safety Follow-up or at the end of Prospective Observation Period if panitumumab was not administered in the last 4 weeks of observation	
Prospective Observation Period	Period between Enrolment and start of Safety Follow-up defined as 1) 15 months of continuous 1st line panitumumab plus chemotherapy treatment administration or 2) up to 15 months after stop of 1st line treatment without subsequent 2nd line treatment or 3) 1st line panitumumab plus chemotherapy until progression/start of 2nd line treatment or death or withdrawal of informed consent or loss-to follow-up, whichever occurs first	

Product: Panitumumab (Vectibix®) Protocol Number: 20170734 POWER Date: 29 April 2019

Date: 29 April 2019 Page 10 of 64

Abbreviation or Term	Definition/Explanation
Retrospective Period	Period between start of 1 st line panitumumab plus chemotherapy and enrolment

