9.1 Study Design

This is a multicentre, ambidirectional (retrospective-prospective), observational study in the selected European countries, including but not limited to Austria, Bulgaria, Croatia, Czech Republic, Hungary, Poland, Slovenia, Romania and Russia.

The Study Design Schema is presented in Figure 1. In general, to gather the most comprehensive and recent data, the study consists of 3 phases: Retrospective Period, Prospective Observation and Safety Follow-up. Retrospective data will be collected from

Date: 29 April 2019 Page 22 of 64

1 to a maximum of 12 months preceding enrolment, Prospective Observation will be led by a maximum of 15 months and a Safety Follow-up of 30 days after the end of the observation, giving a total of a maximum 28 months of mCRC management data.

Subjects with initially non resectable WT *RAS* mCRC receiving panitumumab in combination with chemotherapy as first-line treatment will be eligible for the study. The decision on treatment with panitumumab should have been taken independently and prior to the decision to study enrolment.

Study participants must have received at least one dose of panitumumab in combination with chemotherapy between 1 and 12 months before enrolment (defined as the informed consent [ICF] signature date). Panitumumab as a 1st line treatment in combination with

chemotherapy should be ongoing at enrolment. Therefore, the Retrospective phase will last a maximum of 12 months for an individual subject. An Interactive voice response system (IVRS) system will be used for enrolment. Baseline data including demographics, characteristics and subjects' clinical information will be collected retrospectively from medical records up to the point of enrolment. From the enrolment point, prospective data will be recorded. The Prospective phase will consist of two periods: 1) observation during the 1st line treatment administration and 2) observation after the end of 1st line treatment. The maximum duration of the Prospective phase will be 15 months. In case of a change in therapy and 2nd line treatment implemented, subjects will enter into the Safety Follow-up phase.

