9.2.3 Subject/Healthcare Professional Eligibility

9.2.3.1 Inclusion Criteria

- I. Subject who received first infusion of panitumumab in combination with chemotherapy as 1st line treatment between 1 and 12 months before enrolment and who is continuing on treatment with panitumumab in combination with chemotherapy at the time of enrolment
- II. Subject with a record of WT RAS CRC diagnosis as per standard clinical practice
- III. Subject with metastatic carcinoma of the colon or rectum with at least one metastatic site recorded

Date: 29 April 2019 Page 26 of 64

IV. Subject with initially non resectable mCRC at the start of panitumumab plus chemotherapy treatment

- V. Subject who was diagnosed with a tumour, assessed by CT/MRI etc. prior to panitumumab plus chemotherapy initiation
- VI. Histologically or cytologically confirmed carcinoma of the colon or rectum as the primary site
- VII. Subject ≥ 18 years of age on the date of enrolment/ICF signature
- VIII. Subjects whose care will be managed primarily by the enrolling physician and/ or all records will be available from initiation of 1st line panitumumab plus chemotherapy treatment
- IX. Subject or subject's legally acceptable representative has provided informed consent

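### Dose and schedule changes in 1st line treatment, a primary outcome, are summarised as percentages over a period whose ceiling from first dose runs from 16 to 27 months with enrolment lag, so the percentages have no defined time horizon

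*Protocol*

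**What the plan says.** Table 2 and section 9.3.2 of the protocol make changes in 1st line dose and infusion schedule a primary outcome. Table 2 reports it by country, tumour side and chemotherapy backbone, as well as in total.

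Section 9.2.3.1 admits subjects whose first infusion was "between 1 and 12 months before enrolment and who is continuing on treatment with panitumumab" plus chemotherapy. Section 9.1 sets the data span at "1 to a maximum of 12 months preceding enrolment, Prospective Observation will be led by a maximum of 15 months", and with Safety Follow-up arrives at "giving a total of a maximum 28 months of mCRC management data". Under the definition in section 2, observation can end sooner, for example "1st line panitumumab plus chemotherapy until progression/start of 2nd line treatment or death or withdrawal of informed consent".

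Dosing changes are abstracted back to first dose (section 9.2.5) and then recorded monthly after enrolment (section 9.2.6). Section 9.7.2.2 uses both periods in the analysis. Section 9.7.2.3.2 places the start of the Observation Period at first dose; it speaks of "subject status at the start of the Observation Period (Baseline", where Baseline is the date of first dose.

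For the analysis, section 9.7.2.4 says the 1st line description "will be summarized across the entire observation period using descriptive statistics". Section 9.7.2.1 adds: "Counts and percentages will be provided for categorical outcomes". That section also allows logistic or general linear models with stepwise elimination at 5%, to show which covariates influence treatment pattern. The covariate list in section 9.3.3 includes country. It includes neither enrolment lag nor exposure time.

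**The concern.** A percentage with at least one change means something only over a stated length of time. Here a subject enrolled 1 month after first dose brings 1 month of past treatment, and one enrolled at 12 months brings 12. Both may then be followed for another 15. The second subject has had longer to accumulate a change, even if both are managed identically. The pooled percentage therefore answers no definite question, such as how many patients have a change within 6 or 12 months.

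If typical lag differs between countries or subgroups, part of any difference in the percentages, or of any covariate kept by the stepwise models, would reflect when subjects were enrolled and not how they were treated.

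**Working it through.** **Window.** The plan's own figure reproduces: 12 months retrospective + 15 prospective + 1 of Safety Follow-up = 28 months. Without Safety Follow-up, the ceiling from first dose is 1 + 15 = 16 months at the shortest lag and 12 + 15 = 27 months at the longest.

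**Yardsticks.** For 600 subjects the 95% half-width at 50% is 1.96 × √(0.25/600) = 4.0 points, as the Abstract states. For an average country (600/9 ≈ 67 subjects, equal split assumed) it is 1.96 × √(0.25/67) ≈ 12 points.

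**Dose or schedule change.** The protocol gives no rates, so the following are assumptions:
- median time on 1st line treatment of 6, 10 or 14 months
- 30% or 50% with a change by 12 months on treatment
- change hazard constant, or front-loaded (Weibull shape 0.5)
- discontinuation hazard constant, or rising (Weibull shape 1.5)
- changes occur only on treatment and are independent of discontinuation

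Let L be the lag, T the remaining time on treatment given still on treatment at L, and Sc the probability of no change by a given time on treatment. Then

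P(any change) = 1 − E[Sc(L + min(T, 15))].

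With constant hazards h (change) and λ (discontinuation) this is

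1 − e^(−hL) × [λ/(λ+h) × (1 − e^(−15(λ+h))) + e^(−15(λ+h))].

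Take the central case of median 10 months and 50% by month 12. Then λ = ln2/10 = 0.0693, h = ln2/12 = 0.0578 and e^(−15 × 0.1271) = 0.149. The bracket is 0.545 × 0.851 + 0.149 = 0.613.

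| Lag (months) | e^(−hL) | Any change |
|---|---|---|
| 1 | 0.944 | 42.1% |
| 3 | 0.841 | 48.5% |
| 9 | 0.595 | 63.5% |
| 12 | 0.500 | 69.3% |

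The gap is 27 points between lags 12 and 1, and 15 points between lags 9 and 3. Expected 1st line exposure is L + (1 − e^(−15λ))/λ, which is 1 + 9.3 = 10.3 months at lag 1 and 12 + 9.3 = 21.3 months at lag 12.

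The extremes over all combinations are:

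| Case | Lag 1 | Lag 3 | Lag 9 | Lag 12 | 12 vs 1 | 9 vs 3 |
|---|---|---|---|---|---|---|
| Smallest: median 14, 30% by month 12, front-loaded changes, rising discontinuation | 29.0% | 30.6% | 35.1% | 37.1% | 8 | 4.5 |
| Largest: median 6, 50% by month 12, both hazards constant | 34.7% | 41.9% | 58.9% | 65.4% | 31 | 17 |

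**Cessation of 1st line treatment.** Every subject is one "who is continuing on treatment with panitumumab in combination with chemotherapy at the time of enrolment", so nobody is at risk of stopping before enrolment. The window is at most 15 months at every lag, and the share stopping in it is 1 − S(L+15)/S(L).
- Constant hazard, median 10 months: 1 − 2^(−1.5) = 64.6% at every lag, a gap of zero.
- Weibull shape 1.5, median 10 months: 74.9% at lag 1 and 88.5% at lag 12.
- Shape 1.5 with medians of 6 to 14 months: gaps of 4 to 16 points.

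Here lag acts only through left truncation combined with a hazard that changes with time since first dose.

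**The case against.** The strongest objection is that crude percentages are partly inferred. The sentence in section 9.7.2.4 says descriptive statistics and does not itself name a share with any change. Section 9.7.2.1 has a general Kaplan-Meier rule for time-to-event data, section 9.3.1 computes exposure from first dose to discontinuation, and section 9.7.1 leaves details to the SAP. All of that is true, and it leaves room for a better summary. But the protocol already fixes the window, the type of summary for categorical outcomes and the covariate list, and it does not tie exposure to the change summary. An SAP that follows this text would reproduce the problem.

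The period itself is also ambiguous. Section 9.2.6 uses the term for the 15 months after enrolment, which would give one ceiling for all. Sections 9.3.1, 9.7.2.2 and 9.7.2.3.2 point to the combined period.

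Three stronger readings are tempting, and the documents do not support them:
- *Cessation percentages also run over 16 to 27 months.* They do not, because treatment must be ongoing at enrolment.
- *Country differences in the results will be produced by lag.* Recent reimbursement (section 7.2) and differing policies (section 9.9.1.1) make different lags possible. The protocol gives no lag distribution, and lag is capped at 12 months everywhere.
- *Subjects lost or withdrawn are counted as having no change.* No passage says so, and section 9.7.2.2 shows missing categorical responses as a separate category.

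The size is also uncertain. Section 7.1 puts the first skin symptom at a median of 10 days, so front-loaded changes are plausible, and these give the smaller gaps.

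**Conclusion.** The point holds for dose and schedule changes, and it should be fixed because treatment pattern is a primary objective. With identical practice the share with any change rises with lag by about 8 to 31 points between the extremes and 4.5 to 17 points between lags of 3 and 9 months. The planned half-width is 4 points overall; for a single average country the fairer yardstick is about 12.

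The sizes rest on assumed rates. Provided changes are independent of discontinuation, the direction does not depend on them. If subjects with changes tend to stop earlier, the gap would be smaller. The 16 to 27 months is a ceiling, since observation often ends sooner.

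That the pooled percentage has no time horizon holds whatever the lag distribution. Distortion of country or subgroup comparisons is conditional on lag differing between groups. For cessation, the effect is 0 to 16 points, depending on whether the hazard changes with time on treatment.

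**What to change.** In section 9.7.2.4:

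1. State that the period for treatment changes runs from first dose to the end of 1st line exposure as computed in section 9.3.1.
2. Report dose and schedule changes as the number of changes per month of that exposure. Where change dates are available, also report the proportion with a change by a fixed time from first dose, for example 6 and 12 months.
3. Report time to cessation from first dose, with entry to the risk set at enrolment and censoring at last contact.
4. Show enrolment lag and observed exposure by country, and add exposure time to any model of treatment changes under section 9.7.2.1.
5. Keep the plain percentages as supplementary output.

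The cost is a few extra tables and no extra subjects. There are two limits. Exact dose dates are not collected, and the retrospective data list in section 9.2.5 does not name change dates, so fixed-time estimates may be coarse or unavailable for late enrolees. A per-month rate also stays partly dependent on lag if changes are concentrated early in treatment, which is why lag and exposure should be shown beside it.
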